#### 6.7.4. CCI

CCI will be performed at select US trial sites for patients who agree to provide separate ICF/Assent for this assessment.

CCI and will occur at the time points designated in the SoAs (Table 1, CCI). If DXA is not available at the clinic, this procedure may be skipped, with prior approval of the Sponsor.

For CCI methodology, CCI

The risk associated with exposure to ionizing radiation is minimal and further minimized through the exclusion of pregnant women and the requirement to collect an additional consent/assent for this assessment.

If patients have severe obesity and cannot be measured in the CCI available due to practical limitations CCI, then this assessment can be skipped.

## 6.8. Safety Assessments

### 6.8.1. Vital Signs

Vital signs include systolic and diastolic blood pressure (BP), heart rate (HR), respiration rate (RR; breaths/minute), and body temperature (°C). Vital signs will be obtained in the sitting position following at least 5 minutes of rest each time point designated in the SoAs (Table 1, CCI).

All BP and HR measurements will be taken in triplicate, approximately 2 minutes apart. When possible, BP should be taken in the non-dominant arm throughout the trial, using the same methodology (automated or manual). Repeat measures and more frequent monitoring can be implemented for significant increases in BP or HR.

### 6.8.2. Ambulatory BP Monitoring (ABPM)

At select sites in North America and Europe, ABPM will be conducted outside of the clinic setting in all patients  $\geq 4$  years of age. For patients  $\leq 12$  years of age, both caregiver and Investigator will confirm feasibility of patient compliance in this assessment. The ABPM monitor will measure BP (systolic and diastolic) and HR in 30-minute intervals for each 24-hour period. ABPM assessments will require patients to wear the monitor at each time point (per SoA) below for any 24-hour period before each of the following visits:

- Day 1 (conducted during Screening)
- Week 24

- The EOT Visit

CCI

### 6.8.3. Physical Examinations

A complete physical examination will be conducted at Screening, at the EOT Visit and at the ETT, as applicable. At other time points, as designated in the SoAs (Table 1 CCI), an abbreviated examination will be performed.

- A complete physical examination will include review of peripheral lymph nodes; head; eyes (including conjunctiva); ears; nose; mouth and oropharynx; neck; heart; lungs; abdomen; musculoskeletal including back and extremities; and neurologic examination.
- The abbreviated examination should focus on heart, lungs and skin, and any areas of previous abnormal findings, noting any changes from baseline.
- Tanner Staging for assessment of pubertal development will be conducted for those patients who have yet to reach Tanner Stage V (at V1, EOT or ETT, as applicable). If a female patient reaches menarche during the trial, the Tanner exam after V1 can be skipped.

Whenever possible, the same trained health care professional will conduct the examination and Tanner Staging.

All physical examinations are to be conducted in adequate light.

Changes from baseline in any physical examination findings identified by the Investigator as clinically significant must be recorded as an AE on the appropriate electronic case report form (eCRF).

### 6.8.4. Comprehensive Skin Examinations

A comprehensive skin examination will be performed by the Investigator at the time points designated in the SoA (Table 1, CCI). The skin examination should include a full body (head-to-toe skin examination). If any concerning lesions are identified during Screening, the patient should be referred to a dermatologist. Any concerning lesions will be biopsied by the dermatologist and results must be benign prior to the first dose of setmelanotide. If the pre-treatment biopsy results are of concern, the patient will be excluded from the trial. Additionally, any concerning lesion or change in an existing lesion during the course of the trial must be evaluated by the dermatologist and biopsied, if clinically indicated in the opinion of the dermatologist.

### 6.8.5. Electrocardiograms

A single 12-lead ECG will be performed at the time points designated in the SoA (Table 1, CCI). ECGs are to be performed with the patient in the supine position following a period of at least 10 minutes of rest. The ECG will be performed after vitals are collected and before any other procedures that may affect heart rate, such as blood draw. A printout of the ECG traces will

be made available for safety review by the investigator and maintained with source documentation. Clinically significant ECG abnormalities that occur during the study will be recorded as AEs.

#### 6.8.6. Clinical Laboratory Tests

Blood and urine samples for clinical laboratory tests are to be collected at the time points designated in the SoAs (Table 1, CCI) and analyzed at a central laboratory (with the exception of urine pregnancy tests, which may be performed at home, as applicable). For purposes of study conduct, only laboratory tests analyzed in the central laboratory may be used. Local laboratories may be used at the discretion of the investigator to monitor urgent medical issues. If a local laboratory value is abnormal and clinically significant, it will be verified by the central laboratory as soon as the investigator becomes aware of the abnormal result. If it is not possible to send a timely sample to the central laboratory, the investigator may base an AE on the value of the local laboratory test. Samples are to be collected prior to trial drug administration.

All clinically significant laboratory abnormalities will be followed-up by repeat testing and further investigated according to the judgment of the Investigator. The Investigators will adhere to the site-specific blood volume limits for safety laboratory and PK analyses both to ensure minimal distress and reduce the number of venipunctures in pediatric patients (Refer to Appendix 2).

The safety laboratory test panels are shown in Table 7.

**Table 7. Safety Laboratory Test Panels**

Serum Chemistry	Hematology	Urinalysis b
Glucose	Hematocrit	Color
Blood urea nitrogen	Hemoglobin	Clarity
Uric acid	CCI	Leukocyte esterase
Creatinine	Mean Corpuscular Hemoglobin	Nitrite
Creatine phosphokinase	Erythrocytes	Urobilinogen
Sodium	Mean Corpuscular Volume	Urine protein
Potassium	Platelets	pH
Chloride	Leukocytes	Specific gravity
Bicarbonate	Differentials (absolute and percent):	Urine ketones
Calcium	Basophils	Urine bilirubin
Lactate dehydrogenase	Eosinophils	Urine glucose
Magnesium	Neutrophils	Blood
Phosphate	Lymphocytes	
Total bilirubin	Monocytes	
Direct bilirubin		
Alkaline phosphatase		
Alanine transaminase		
Aspartate transaminase		

Serum Chemistry	Hematology	Urinalysis b
Albumin Gamma-glutamyl transferase Total protein CCI    		

c If urinalysis results are positive on a urine dipstick for leukocyte esterase, nitrites, protein, or blood, microscopic examination of urine will be performed, and results will be provided.

### **Additional Tests at Screening:**

The following tests will be performed during Screening to assess eligibility:

- Levels of serum follicle-stimulating hormone (FSH) for suspected postmenopausal women who have been post-menopausal >12 months and should be in post-menopausal range. FSH is not required at screening for females with tertiary and/or secondary hypogonadism who are on hormonal replacement therapy for this condition.
- Urine beta-human chorionic gonadotropin ( $\beta$ -hCG) for Women of Childbearing Potential (WOCBP). The pregnancy tests must be negative before the Day 1 dosing.

### **Thyroid Tests at Screening:**

- T4, Free T4, and T3 will be measured at Screening.

### **Additional Tests Throughout Trial**

#### **1) Pregnancy Testing for WOCBP (as defined in Section 6.8.9):**

- A urine pregnancy test may be performed to expedite availability of results prior to dosing on Day 1. All in-clinic pregnancy tests per SoAs (Table 1, CCI) will be serum tests and analyzed at the central laboratory; dosing may continue with results pending. At telehealth visits, urine pregnancy tests will be performed using pregnancy test kits. Additional pregnancy tests may be required according to local regulations and/or requirements.
- Pregnancy testing is not required for females with tertiary and/or secondary hypogonadism who are on replacement therapy for this condition and are not on ovarian stimulation therapy. Pregnancy testing may be conducted at the discretion of the investigator.

#### **2) CCI**

#### **3) Hormone Testing**

- IGF1 labs will be drawn at Baseline and approximately every 3 months for patients taking growth hormones.
- Estradiol and testosterone labs will be drawn for all patients at Baseline (V1), EOT, and ETT (as applicable).

If the testing occurs during a permitted telehealth visit, that visit will be required in person.

#### 4) Additional Evaluations

Additional clinical laboratory evaluations will be performed at other times if judged to be clinically appropriate.

### **Bridging Visits**

For patients who transition to Bridging visits, specific labs will be collected as indicated in the SoA (Table 1, CCI [REDACTED]).

#### **6.8.6.1. CCI [REDACTED]**

### **6.8.7. Pharmacokinetics and Anti-Drug Antibodies**

#### **6.8.7.1. Pharmacokinetics**

Blood samples for determination of setmelanotide levels in plasma at trough will be collected as indicated in the SoAs (Table 1, CCI [REDACTED]). Samples for PK (trough) and anti-drug antibodies (ADA) will be collected on the same schedule during the trial. All samples should be collected before trial treatment administration on the day of collection. For all blood samples for PK analysis, the actual (clock) time each PK blood sample and the time of the last dose will be recorded in the source documents and eCRF. Plasma will be harvested from each blood sample collected for PK analysis and the plasma will be frozen, shipped to a bioanalytical laboratory designated by the Sponsor, and analyzed for setmelanotide concentrations.

Setmelanotide plasma PK will be assessed in all patients by trough (pre-dose) concentrations measured prior to dose administration in the clinic as per the SoAs.

The trough concentration values will be reported descriptively as mean, standard deviation (SD), maximum (Max), minimum (Min), median, and percent coefficient of variation (%CV) based on dose and visit.

#### **6.8.7.2. ADA**

Blood samples for analysis of ADAs (anti-setmelanotide and anti- $\alpha$ MSH) will be collected at the time points specified in the SoA. Samples for ADA and PK (trough) will be collected on the same schedule during the trial. All samples should be collected before trial treatment administration on the day of collection. Any patient with a positive anti-setmelanotide ADA will

be followed every 3 months after the ADA sample analysis until resolution of the ADA (ie, no measurable ADA response).

#### **6.8.8. Injection Site Examination**

Injection sites will be carefully inspected, evaluated, and scored during the trial period. The injection site evaluation and scoring (by the clinical staff) will include identification and measurement of areas of erythema, edema, and induration, as well as the presence of localized pain, tenderness, and itching. Additional evaluation data can be collected at any visit in which there are injection site reactions, even if not a time point for formal assessment.

A sample injection site evaluation form is included in [Appendix 4](#).

In addition, unscheduled evaluations may also be recorded as warranted by clinical conditions.

#### **6.8.9. Pregnancy and Contraception**

In animal reproduction studies, setmelanotide was not teratogenic at doses >10 times the maximum recommended human dose of 3 mg QD. No evidence of embryo-fetal toxicity was observed. Pre- and postnatal development studies in rats showed no adverse setmelanotide-related effects. Please refer to the IB for additional information.

WOCBP, defined as fertile, following menarche and until becoming post-menopausal unless permanently sterile (hysterectomy, bilateral salpingectomy, or bilateral oophorectomy) must not be pregnant and must have a negative serum pregnancy test result at the Screening Visit. A urine pregnancy test may be performed to expedite availability of results prior to dosing on Day 1. Serum pregnancy testing will also be performed during the trial at the time points specified in the SoA. At sites where pregnancy tests are required for tele-health visits, WOCBP will be given urine pregnancy tests for use at the following visits: Visits 2, 6, 8, 10, 12, and 14 **CCI** (if these visits are conducted as remote visits with visiting nurses).

Furthermore, it is imperative that all trial patients adhere to the contraception requirements as outlined below.

For WOCBP childbearing potential, a highly effective form of contraception (as defined in the Inclusion Criteria, (Section [4.1](#)) must be used/practiced throughout the trial and for 90 days following the trial.

- Combined (estrogen and progestogen containing) hormonal contraception associated with inhibition of ovulation (oral, intravaginal, or transdermal)
- Progestin-only hormonal contraception associated with inhibition of ovulation (oral, implantable, or injectable)
- IUD
- Intrauterine hormone-releasing system
- Bilateral tubal occlusion

- Vasectomy/vasectomized partner (provided that the vasectomized partner is the sole sexual partner of the female participant, and the vasectomized partner has received medical assessment of surgical success)
- Sexual abstinence, only if it is the preferred and usual lifestyle of the patient

Female participants of non-childbearing potential, defined as: permanently sterile (status post hysterectomy, bilateral oophorectomy, or bilateral salpingectomy), or postmenopausal for at least 12 months (and confirmed with a screening follicle-stimulating hormone level in the postmenopausal lab range) do not require contraception during the trial. Younger female patients who have not achieved sexual maturity at trial entry will be assessed for Tanner Staging and required to comply with contraception requirements at first menarche.

Females with tertiary and/or secondary hypogonadism on hormonal replacement therapy for this condition and not receiving fertility treatment (ovarian stimulation) do not meet the criteria of WOCBP, unless otherwise determined by the Investigator.

Male participants with female partners of childbearing potential must agree to use a highly effective method of contraception if they become sexually active during the trial or within 90 days following their participation in the trial. Male patients must also not donate sperm during and for 90 days following their participation in the trial.

If a pregnancy should occur while a male or female patient is on trial treatment, relevant pregnancies will be followed up on to determine birth and neonatal outcomes.

Males with tertiary and/or secondary hypogonadism on hormonal replacement therapy are not considered fertile and do not need to comply with contraception requirements, unless otherwise determined by the Investigator.

#### **6.8.10. Suicidal Ideation and Depression Monitoring**

All 3 questionnaires, the C-SSRS, the PHQ-9/PHQ-A, the CDI-2 should be completed prior to the morning dose at the clinic or in the presence of trained nursing or site staff during telehealth visits, as applicable (as scheduled per SoA).

A patient should be referred to a mental health professional (MHP) if he/she has:

- A PHQ-9/PHQ-A score  $\geq 10$ .
- Any suicidal behavior.
- Any suicidal ideation of type 4 or 5 on the C-SSRS.
- A CDI-2 T-score  $\geq 65$

An AE should also be reported for PHQ-9/PHQ-A  $\geq 10$  or a CDI-2 T-score  $\geq 65$  or a C-SSRS of type 4 or 5.

A referral to an MHP should be recorded as an AE and should also be made if in the opinion of the Investigator it is necessary for the safety of the patient. If a patient's psychiatric condition can be adequately treated with psychotherapy and/or pharmacotherapy, then the patient, at the discretion of the MHP, may be continued in the trial.

In patients with cognitive impairment or pediatric patients, the ability to complete the C-SSRS or PHQ-9 may be limited. If in the clinical opinion of the Investigator a specific patient cannot complete the instrument(s), the following strategies may be employed:

- Site staff may administer the questions directly to the patient or may ask for the information from a third party, such as a caregiver or family members, as appropriate.
- The Investigator may use his/her clinical judgment to skip any questionnaires that he/she feels are not appropriate for a specific patient.

Any deviation from the intended use of an instrument should be documented by the Investigator, along with the reason for the deviation. If the PHQ-9 and C-SSRS are not administered, the Investigator should document that the issues of depression and suicidality were assessed clinically (eg, discussion with caregivers).

See [Appendix 8](#) for the pre-dose timing, location, and format of the Patient and Safety Questionnaires.

#### 6.8.10.1. Columbia-Suicide Severity Rating Scale (C-SSRS)

##### *Patients ≥6 years of age*

As required in the US by the Food and Drug Administration (FDA), for clinical trials of CNS-acting medications, changes in suicidality as assessed by the C-SSRS will be monitored over the course of the trial to ensure patient safety.

The C-SSRS is a tool used not only to predict suicide attempts but to assess the full range of evidence-based ideation and behavior items, with criteria for next steps (eg, referral to an MPH). There are 2 versions of the C-SSRS that will be administered according to the SoAs ([Table 1, CCI](#)).

- **The Baseline/Screening version** of the scale is the initial form of the instrument to assess suicidality in a patient's lifetime. This version can assess a patient's lifetime suicidality for data collection purposes as well as eligibility based on inclusion/exclusion criteria.
- **The Since Last Visit version** of the scale assesses suicidality since the patient's last visit. This version is meant to assess patients who have completed at least 1 initial C-SSRS assessment and should be used in subsequent visits. The 'Since Last Visit' version of the C-SSRS is asking about any suicidal thoughts or behaviors the patient/participant may have had since the last time the C-SSRS was administered.

To be eligible for the trial, a patient cannot have a suicidal ideation of type 4 or 5 at Screening, a suicide attempt during the patient's lifetime, or any suicidal behavior in the last month.

Any patient who reports suicidal behavior or suicidal ideation of type 4 or 5 on the C-SSRS during the trial will be captured as an AE and referred to an MHP.

The C-SSRS should be completed before dosing either in clinic or in the presence of trained nursing or site staff during telehealth visits, as applicable.

#### **6.8.10.2. Patient Health Questionnaire-9 (PHQ-9 or PHQ-A)**

The PHQ-9 is a 9-item depression scale of the Patient Health Questionnaire. The PHQ-9 is a tool for assisting clinicians in diagnosing depression as well as selecting and monitoring treatment. The PHQ-A is a modification of the PHQ-9 for adolescents. After the patient has completed the PHQ-9 or PHQ-A questionnaire, it is scored by the trial staff.

The PHQ-A will be administered to patients 11 to 17 years of age and the PHQ-9 will be administered to patients  $\geq 18$  years of age.

The PHQ-9 or PHQ-A will be implemented at the time points designated in the SoAs (Table 1, CCI ).

In order to be eligible for the trial, the patient must have a Screening PHQ-9/PHQ-A score  $< 15$ . If at any time during the trial an individual patient's PHQ-A or PHQ-9 score is  $\geq 10$ , an AE should be recorded, and the patient should be referred to an MHP.

The PHQ-9/PHQ-A questionnaires should be completed before dosing either in clinic or in the presence of trained nursing or site staff during telehealth visits, as applicable.

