- 28 Injection site evaluations and scoring (by the clinical staff) will include identification and measurement of areas of erythema, edema, and induration, as well as the presence of localized pain, tenderness, and itching. Additional evaluation data can be collected at any visit in which there are injection site reactions, even if not a time point for formal assessment.
- 29 A question querying whether the patient completed their daily injection will be asked via an e-diary. Patients in Bridging visits will record compliance on paper forms.
- 30 AEs will be recorded from the time a patient provides informed consent. AEs reported after dosing on Day 1 will be considered TEAEs.
- 31 At applicable sites measuring ABPM, this assessment will be conducted outside of the clinic setting in patients  $\geq 4$  years of age, (See Section 6.8.2 for patients  $< 12$  years of age and regional applicability). ABPM assessments will require wearing the device at each time point for any 24-hour period prior to: the Day 1 Visit (from last day in Screening window), the Week 24 Visit, and the EOT Visit (occurs after 52 weeks on a therapeutic dose). The ABPM device will measure BP (systolic and diastolic) and heart rate (HR) in 30-minute intervals for each 24-hour period. CCI [REDACTED] arate
- ICF/Assent for this assessment. A CCI [REDACTED] will be taken at the Day 1 Visit. If CCI [REDACTED] is not available at the clinic, this procedure may be skipped. If a patient discontinues before the EOT Visit, CCI [REDACTED] should be performed at the ETT Visit. See Section 6.7.4.
- 33 CCI [REDACTED]
- 34 Lab tests to be conducted only as needed at the discretion of the Investigator.

CCI

CCI

CCI

[figure not shown]

CCI

[figure not shown]
CCI

CCI

[figure not shown]
CCI

CCI

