

• Any clinically significant abnormal laboratory findings or other abnormal safety assessments which are associated with the underlying disease, unless judged by the investigator to be more severe than expected for the patient’s condition.

• The disease/disorder being studied or expected progression, signs, or symptoms of the disease/disorder being studied, unless more severe than expected for the patient’s condition.

• Medical or surgical procedure (eg, endoscopy, appendectomy): the condition that leads to the procedure is the AE.

• Situations in which an untoward medical occurrence did not occur (social and/or convenience admission to a hospital).

• Anticipated day-to-day fluctuations of pre-existing disease(s) or condition(s) present or detected at the start of the trial that do not worsen.

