##### 4.5.2. Adverse Events

All AEs will be coded using the MedDRA coding system (Version 24.0 or later) and displayed in tables by treatment received and in data listings using system organ class and preferred term. AE grade assessment will be based on investigator reporting using the National Cancer Institute Common Terminology Criteria for Adverse Events (NCI-CTCAE), Version 5.0.

Analyses of AEs will focus on those events that are considered treatment-emergent, where treatment-emergent is defined as any AE with onset after the administration of study medication through the end of the study (14 days after last dose administered), any event that was present at

baseline but worsened in intensity or was subsequently considered drug-related by the Investigator through the end of the study, or any event deemed to be related to study drug exposure.

The number and percentage of pivotal and all patients with any treatment-emergent AE (TEAE), with any TEAE assessed by the Investigator as related to treatment (definite, probable, or possible relationship), with any serious TEAE, with any serious related TEAE, with any TEAE leading to study drug withdrawal, or with any TEAE leading to death will be summarized by treatment received, as needed. The aforementioned summaries will be repeated for Japanese patients, as needed.

The number and percentage of pivotal and all patients with treatment-related TEAEs leading to study discontinuation and non-serious TEAEs will also be summarized by treatment received, as needed.

TEAEs of special interest (Nausea, Vomiting, Diarrhea) will be identified and summarized by treatment received for pivotal and all patients, as needed. A separate summary will be provided for Japanese patients.

In these tabulations, each patient will contribute only once (i.e., the most related occurrence or the most intense occurrence) to each of the incidence rates in the descriptive analysis, regardless of the number of episodes.

All AEs occurring on-study will be listed in patient data listings. Listings will also be provided for the following: drug product related TEAEs, serious TEAEs, drug product related serious TEAEs, TEAEs leading to study drug withdrawal, events of special interest, and deaths.

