#### **4.5.4. Patient Health Questionnaire (PHQ-9 or PHQ-A)**

The PHQ-9 is a 9-item depression scale of the Patient Health Questionnaire used to assist clinicians in diagnosing depression as well as selecting and monitoring treatment and is administered to patients ≥18 years old. The PHQ-A is a modification of the PHQ-9 for adolescents (patients ages 11 to 17 years old). Each question has a score from 0 to 3, and all 9 scores are added to produce a total score.

The Patient Health Questionnaire-9 and PHQ-A will be measured as shown in the SoA (Table 1-1). The actual values and change from baseline of the total scores will be summarized with descriptive statistics by visit for pivotal and all patients, as needed.

A by-patient listing of the results of the individual 9 questions will be provided.

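### Depression scores permitted at entry can trigger adverse events on study without reference to baseline, and the plan does not settle whether an unchanged score is treatment-emergent

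*Protocol*

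**What the plan says.** **Entry.** Protocol 6.8.10.2: "In order to be eligible for the trial, the patient must have a Screening PHQ-9/PHQ-A score" below 15. Exclusion criterion 4 in Protocol 4.2 agrees, and it excludes a screening CDI-2 T-score of 70 or more. PHQ 10 to 14 and T-scores of 65 to 69 may therefore enter.

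**Trigger on study.** Protocol 6.8.10: "An AE should also be reported for PHQ-9/PHQ-A" of 10 or more, or for a CDI-2 T-score of 65 or more. Section 6.8.10.2 repeats this for PHQ ("an AE should be recorded, and the patient should be referred to an MHP") and 6.8.10.3 for CDI-2. Section 6.8.10 adds that the referral to a mental health professional (MHP) is itself to be recorded as an AE. None of these passages mentions the baseline score.

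**Treatment emergence.** Protocol Table 1, footnote 30: "AEs reported after dosing on Day 1 will be considered TEAEs"; 6.10 and 6.10.1 say the same. But 6.10.1 also sends medical occurrences that began before treatment to medical history rather than the AE page. Appendix 5 lists among events that are not AEs: "Anticipated day-to-day fluctuations of pre-existing disease(s) or condition(s) present or detected at the start of the trial that do not worsen". SAP 4.5.2 counts an AE with onset after dosing, any event deemed related to study drug exposure, and an event present at "baseline but worsened in intensity or was subsequently considered drug-related by the Investigator".

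**Planned outputs.** SAP 4.5.4 for PHQ: "The actual values and change from baseline of the total scores will be summarized with descriptive statistics by visit". SAP 4.5.5 plans the same for CDI-2.

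**The concern.** The entry ceiling lies above the AE trigger, and the trigger is blind to baseline. A patient who enters at PHQ 12 and stays at 12 meets the trigger at every visit without any change in mood. Whether that patient appears in the TEAE table depends on which passage the site follows when it dates the onset.

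The chance to meet the trigger recurs. PHQ and CDI-2 are scheduled at every clinic visit from V2 to V15 or V16, which is 14 or 15 post-dose occasions, and one score at or above the trigger suffices. The SAP's date rule leans the same way, since SAP 3.10.4 codes a missing onset date as the day of treatment.

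At stake is the readability of the mood rows in the AE tables. Protocol 5.4.4 gives detection of CNS safety effects as the reason for these questionnaires. Unchanged entry scores mixed with new or worsened ones make a true difference between arms harder to see.

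**Working it through.** **1. The plan's own safety figures.** Protocol Table 8 assumes 80 against 40 patients. With the assumed rate p0 in the 40-patient arm and p1 = p0 + d in the 80-patient arm,

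power = Φ{[d − 1.96·√(p̄(1−p̄)(1/80+1/40))] / √(p0(1−p0)/40 + p1(1−p1)/80)}, where p̄ = (40·p0 + 80·p1)/120.

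Solving for d at 80% power gives 22.4, 25.4, 26.6, 26.6 and 25.6 points, against the stated 22.4, 25.4, 26.5, 26.6 and 25.6. The other rows agree to 0.1. No number in the plan is disputed; step 4 uses the same formula.

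**2. One patient, PHQ 12 at Screening, at Day 1 before dosing, and at V2.**

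| Passage | Test applied | Result for this patient |
|---|---|---|
| Protocol 6.8.10, 6.8.10.2 | score of 10 or more | AE, plus a referral AE |
| Protocol Table 1 footnote 30, 6.10 | reported after Day 1 dosing | TEAE |
| Protocol 6.10.1 | began before treatment | medical history, not AE |
| Protocol Appendix 5 | pre-existing, not worsened | not an AE |
| SAP 4.5.2, onset arm | onset dated after dosing | TEAE if the site dates onset at V2 |
| SAP 4.5.2, baseline arm | worsened or considered drug-related | not a TEAE if neither applies |

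No passage says which test governs.

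**3. Effect on the AE comparison if such scores are counted.** Let b be the share entering above the trigger and staying there, and r1 and r0 the true new-event rates (setmelanotide, placebo) among the rest. The documents give none of these, so all are assumptions.

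- Reported rate = b + (1−b)·r.
- Reported risk difference = (1−b)(r1 − r0).

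With r1 = 10% and r0 = 5%:

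| b | Reported rates | Risk difference | Ratio |
|---|---|---|---|
| 0 | 10.0% v 5.0% | 5.0 points | 2.00 |
| 10% | 19.0% v 14.5% | 4.5 | 1.31 |
| 20% | 28.0% v 24.0% | 4.0 | 1.17 |
| 30% | 37.0% v 33.5% | 3.5 | 1.10 |

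With no drug effect and no new events, the carried-over TEAEs would number 8 v 4, 16 v 8 and 24 v 12 in 80 v 40 patients at b = 10%, 20% and 30%. The percentage is the same in each arm, so no false difference is expected.

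**4. Loss of sensitivity for a larger effect.** With r1 = 25% and r0 = 5%, the formula in step 1 gives:

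| b | Power, all scores counted | Power, new crossings only, in (1−b) of each arm |
|---|---|---|
| 0 | 81.4% | 81.4% |
| 10% | 56.5% | 76.5% |
| 20% | 40.6% | 70.5% |
| 30% | 30.4% | 63.5% |

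The AE analysis is descriptive (Protocol 7.6), so power here only indexes how visible a difference would be.

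**5. What the planned tables show.** Under SAP 3.2 the by-visit summaries give n, mean, median, SD, minimum and maximum. None counts patients who newly crossed the trigger. The CDI-2 trigger is a T-score, whereas SAP 4.5.5 summarises total scores. Shift tables are already planned for C-SSRS (SAP 4.5.3), Global Hunger (4.5.6), laboratory data (4.5.9) and examinations (4.5.12), but not for PHQ or CDI-2.

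**The case against.** A reader might infer that an unchanged entry score always becomes a TEAE. The documents do not support that. Both questionnaires are also given before dosing at Screening and Day 1, and AE collection starts at consent. A patient at PHQ 12 has therefore met the trigger before treatment, and 6.10.1 would place the finding in medical history. The SAP's baseline arm would exclude it, and Protocol 7 lets the SAP modify the planned analyses. This objection stands: TEAE status is unsettled. The conflict itself remains.

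A reader might also infer that a real mood signal would be hidden. Randomisation balances carried-over cases in expectation, and the risk difference shrinks only by the factor 1−b. Nor are the instrument outputs limited to means: change from baseline with median, SD and range is planned, along with by-patient listings and a C-SSRS ideation shift table. This stands too, so the effect is dilution of the AE table. The planned summaries still do not show threshold crossings by arm.

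The illustrations rest on assumed inputs, and applying b to all 120 patients is a simplification. PHQ starts at age 11 and CDI-2 covers 7 to under 12, so patients under 7 receive neither. Excluding recent major depressive disorder and severe psychiatric disorders should also limit b. Against that, Protocol 2.1 describes psychosocial disorders including depression in this disease, so entry scores above the trigger are plausible.

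Finally, each patient counts once per incidence rate, so the referral AE need not inflate a given rate. Broad capture of safety events also has value, and for that reason the remedy leaves reporting by sites alone.

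**Conclusion.** The point holds as an unreconciled classification rule and a missing table. The gap between entry limit and trigger, and the absence of any baseline reference, are plain in the text. The documents conflict on whether an unchanged score is treatment-emergent, so identical patients may be classified differently.

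The consequence is dilution of a between-arm difference in mood TEAEs, of unknown size. In the 10% v 5% example the loss is 0.5 to 1.5 percentage points for b of 10% to 30%. That assumes every above-trigger entrant stays above the trigger and is counted as a TEAE, so it is the upper end for a given b. No bias towards either arm is expected. This is an inexpensive improvement to safety reporting and does not touch the efficacy conclusions.

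**What to change.** 1. Reconcile Protocol 6.8.10 and 6.10 with Appendix 5 and SAP 4.5.2. In the TEAE tables, a score-triggered event and the referral that follows it count as treatment-emergent only if the patient was below the trigger at baseline, or worsened from baseline, or the event is considered drug-related as SAP 4.5.2 already provides.
2. In SAP 4.5.4 and 4.5.5 add a by-arm shift table from baseline to worst post-baseline category: PHQ below 10, 10 to 14, and 15 or more; CDI-2 T-score below 65, 65 to 69, and 70 or more. Use T-scores for CDI-2 so that the table is on the trigger's scale.
3. Leave the entry limits, the referral rule and the reporting of scores by sites as they are.

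The cost is a small wording change in protocol and SAP and one more table, from data already collected. The downside is fewer score-triggered TEAEs in the AE table; the shift table keeps the full distribution visible, including patients who entered above the trigger and did not change.
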